1.0 PROTOCOL SUMMARY AND/OR SCHEMA

This is a phase II study testing durvalumab and tremelimumab in metastatic, non-transitional cell carcinoma of the urothelial tract. Patients with I) any component of small cell carcinoma (or neuroendocrine features) II) predominant squamous cell carcinoma or III) predominant adenocarcinoma of the urothelial tract will be enrolled. A Simon's minimax two-stage design will be carried out. We will enroll 13 patients in the first stage. If we see 1 or more responses in the first stage, we continue to the second stage where we enroll an additional 14 patients for a total sample size of 27 patients. Patients will be treated in 4-week cycles. Patients will receive 4 cycles of the combination of durvalumab and tremelimumab followed by up to 9 cycles of durvalumab maintenance or until lack of clinical benefit or unacceptable toxicity. Cross-sectional imaging will be performed every 8 weeks until the end of treatment. The best, confirmed overall response rate (ORR) by RECIST 1.1 will be determined as the primary endpoint.

2.1 OBJECTIVES AND SCIENTIFIC AIMS

Primary Objective:

- To determine the efficacy of the combination of durvalumab and tremelimumab in patients with I) carcinoma with a small-cell component (or neuroendocrine features) II) predominant squamous cell carcinoma or III) predominant adenocarcinoma or the urothelial tract as measured by best ORR, which will include the sum of complete response (CR) + partial response (PR) by RECIST v 1.1.

Secondary Objectives:

- To assess for other parameters of clinical outcome of the combination of durvalumab plus tremelimumab in patients with I) carcinoma with a small-cell component (or neuroendocrine features) II) predominant squamous cell carcinoma or III) predominant adenocarcinoma or the urothelial tract including:
 - Progression Free Survival (PFS) and duration of response (DOR) rate by RECIST v1.1
 - Overall survival (OS)
 - Best ORR (CR + PR), PFS, and DOR by Immune-related Response Criteria in Solid Tumors (irRECIST) criteria
 - Clinical benefit (CR + PR + Stable Disease [SD]) rate by RECIST v1.1 and irRECIST
 - Rate of immune-related Adverse Events (irAE)
 - Rate of serious adverse events (SAE)

Exploratory Objectives:

- To determine differences in the immune microenvironment between bladder cancer histologies as determined by PD-L1 staining, immune related gene expression profiles, and multiplex immunofluorescence (IF) for multiple immune cell subsets
- To determine whether bladder cancer histology and the associated immune microenvironment as defined above is predictive of the clinical benefit rate (CBR).
- To determine if T cell clonality in tumors and blood will be associated with the CBR.
- To determine whether immune suppressive cells types in the peripheral blood and in tumors will correlate with a decreased CBR.

3.1 BACKGROUND AND RATIONALE

3.2 Non-Transitional Cell Carcinoma of the Urothelial Tract

Approximately 90% of malignant tumors arising from the urothelial tract are transitional cell carcinoma (TCC) (1). The remainder encompasses a variety of subtypes such as adenocarcinoma, squamous cell carcinoma, small cell/neuroendocrine carcinoma, sarcoma, paraganglioma, carcinosarcoma/sarcomatoid, lymphoma, or melanoma. Adenocarcinoma, squamous cell carcinoma, small cell/neuroendocrine carcinoma are the most common of these non-TCC histologies and comprise 0.5-2%, 3-5%, and 0.5-1% of bladder tumors, respectively (1). TCC plus squamous cell carcinoma, adenocarcinoma, and small cell/neuroendocrine carcinoma are the recognized as distinct clinical entities (2). Although each of these tumors is characterized by unique risk factors and biology, a unifying feature is their

aggressive course and dismal prognosis, including in patients with organ-confined disease (3) (Figure 1). For patients with metastatic disease, poor outcomes with standard, front-line chemotherapeutic regimes have been reported in two small prospective and a variety of small retrospective studies (Table 1). For patients with metastatic disease that has progressed despite front-line therapy, clinicians have only case reports and a few retrospective studies to guide management. Outcomes are typically poor, and new therapeutic strategies are urgently needed.

[figure not shown]

Figure 1: Non-transitional cell carcinoma is associated with poor outcomes following radical cystectomy (3)

Histology	Regime	ORR (% response ; 95% CI)	Median OS (Months)	Citation
Adeno	TIP	4/11 (36%; 15-59%)	24.8 (95% CI, 10.2 to 32.2)	(4)
Adeno	DMF IA/IV	5/8 (62.5%)	10 (95% CI not reported)	(5)
Adeno	Variable*	3/9 (33%)	20 (95% CI not reported)	(6)
Squamous	TIP	2/8 (25%; 3-65%)	8.9 (95% CI, 5.4 to not reached)	(4)
Squamous	Variable**	0/5	11 (95% CI not reported)	(7)
Small Cell	IA and EP	11/12 (92%)	13.3 (95% CI, 8.5 to not reached)	(8)
Small Cell	Variable^	9/12 (75%)	15 (95% CI not reported)	(9)

Table 1. Frontline Chemotherapy Regimes in Non-Transitional Cell Predominant Metastatic Carcinoma of the Urothelial Tract. TIP=ifosfamide, paclitaxel, and cisplatin; IA=Ifosfamide/Doxorubicin; EP= Etoposide/Cisplatin; DMF= intravenous and/or intra-arterial 5-fluorouracil, doxorubicin, and mitomycin-C; *5-fluorouracil or cisplatin containing regimes; **methotrexate/vinblastine/doxorubicin/cisplatin or 5FU/cisplatin or gemcitabine/cisplatin; ^cyclophosphamide/doxorubicin/vincristine or carboplatin/etoposide, or other platinum -based regime

3.3 Rationale for Immune Checkpoint Blockade in Non-Transitional Cell Carcinoma of the Urothelial Tract

Checkpoint blockade is a transformative therapeutic approach to a broad spectrum of malignancies because it increases the power of antitumor immunity to obtain durable responses. Antibodies targeting the programmed death 1 (PD-1) pathway have demonstrated evidence of activity and been approved by the Federal Drug Administraion (FDA) in untreated and pre-treated metastatic TCC (10–15). Although these agents have not yet been investigated in non-TCC histologies, the promising results in small cell and squamous cell lung cancer (Table 2) provide strong rationale for their use in this setting. With regard to adenocarcinoma of the urothelial tract, a recently presented phase I expansion study incorporating immune checkpoint blockade reported that 1 in 4 patients had a partial response (16). Our group has also had success treating patients with adenocarcinoma of the urothelial tract with anti-PD-1 antibodies (personal communication with [name]). Durvalumab is a anti-PDL1 antibody, which demonstrated a toxicity profile similar to other anti-PD-1/anti-PD-L1 agents, and was recently granted accelerated approval by the FDA for pre-treated metastatic TCC (10).

Although treatment with PD-1 blockade has led to dramatic success in patients with previously incurable metastatic TCC, it is still only a minority of patients who benefit. This finding has driven the field toward developing combination therapies to increase response rates. Tremelimumab is an antibody that blocks cytotoxic T-lymphocyte-associated antigen 4 (CTLA-4), which is expressed on the surface of T cells, where it primarily suppresses their early stages of activation by inducing inhibitory downstream T-cell receptor (TCR) signaling and counteracting activity of the T-cell costimulatory receptor, CD28 (17,18). The combination of CTLA-4 and PD-1 blockade is FDA approved in melanoma and seems to be more efficacious than CTLA-4 blockade alone (19,20) or PD-1 blockade alone in patients whose tumors do not express PD-L1 (19). In patients with previously treated metastatic urothelial carcinoma who received anti-PD-L1 therapy, our group recently demonstrated that the diversity of the baseline peripheral TCR repertoire was directly correlated with overall survival (21). Importantly, CTLA-4 blockade has also been shown to increase the diversity

peripheral TCR repertoire, which may increase the likelihood that a particular anti-tumor T cell population is present (22,23). In addition, anti-PD-1 monotherapy and the combination of CTLA-4 and PD-1 blockade were evaluated in randomized phase II trial in recurrent small cell carcinoma of the lung (24). The combination demonstrated higher response rates over anti-PD-1 monotherapy is now listed in the NCCN compendium guidelines for the treatment of small cell carcinoma of the lung. Finally, in Checkmate 032, combined CTLA-4/PD-1 blockade in patients with previously-treated, metastatic TCC with nivolumab 1 mg/kg and ipilimumab 3 mg/kg led to an ORR of 38.5%, which compares favorably with 24.4% ORR seen with nivolumab monotherapy (25). Although drug-related adverse events of grade 3 or 4 are more common with the combination of PD-1 and CTLA-4 therapies, most of these events resolve with immunosuppressive medication.

Therefore, the anti-PD-L1 antibody durvalumab in combination with the anti-CTLA-4 antibody tremelimumab is a logical therapeutic strategy. We hypothesize that it will demonstrate activity in patients with adenocarcinoma, squamous cell carcinoma, small cell/neuroendocrine carcinoma of the bladder. If successful, the proposed trial could change the standard of care for this patient population with very limited treatment options.

Histology	PD-1 Blocking Agent	ORR	Citation
Small Cell (PD-L1+)	Pembrolizumab	7/20 (35%)	(26)
Small Cell	Nivolumab 3 mg/kg	10/98 (10%)	(24)
	Nivolumab 1 mg/kg + Ipilimumab 3 mg/kg	14/61 (23%)	
	Nivolumab 3 mg/kg + Ipilimumab 1 mg/kg	10/54 (19%)	
Squamous	Nivolumab	17/117 (15%)	(27)
Squamous	Nivolumab	27/135 (20%)	(28)
Squamous	Durvalumab	18/88 (21%)	(29)

Table 2. Immune checkpoint Blockade in Recurrent Small Cell and Squamous Cell Lung Cancer

3.4 Rationale for allowing chemo-naïve patients with squamous cell carcinoma and adenocarcinoma

Atezolizumab (anti-PD-L1) and pembrolizumab (anti-PD-1) both have accelerated approval from the FDA for front-line use in chemo-naïve, cisplatin-ineligible patients with metastatic TCC. Approximately 50% of patients with metastatic TCC are cisplatin-ineligible (30). Pembrolizumab demonstrated a 29% ORR with the median duration of response not yet being reached after a median follow-up of 9.5 months (31). Atezolizumab demonstrated an ORR of 23% with a median overall survival of 15.9 months (14), which compares favorably to the 13.8-14.8 month median overall survival of cisplatin-eligible patients with metastatic TCC treated with a front-line cisplatin based regimens (32). These data have provided the rationale for multiple, randomized, front-line clinical trials evaluating immune checkpoint blockade in patients with metastatic TCC. The squamous cell and adenocarcinoma histologies are generally believed to be chemotherapy refractory. Indeed, the NCCN guidelines suggest that patients with muscle-invasive squamous cell and adenocarcinoma of

the bladder proceed directly to cystectomy without receiving the neoadjuvant cisplatin-based chemotherapy that is standard of care for patients with muscle-invasive TCC. Small cell carcinoma, on the other hand, is well known to be chemotherapy sensitive, although it almost uniformly progresses after treatment. Therefore, we will allow patients with squamous cell carcinoma and adenocarcinoma to be chemo-naïve while patients with small cell/neuroendocrine must have been previously treated.

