6.1 CRITERIA FOR SUBJECT ELIGIBILITY

6.2 Subject Inclusion Criteria

For inclusion in the study, patients should fulfill the following criteria:

1. Age \geq 18 years at time of informed consent
2. Body weight $>$ 30 kg
3. Histologically or cytologically confirmed small cell carcinoma, squamous cell carcinoma or adenocarcinoma (confirmed at MSKCC) of the bladder, ureter, urethra, urachus, or renal pelvis. Patients with squamous cell carcinoma and adenocarcinoma are required to have a predominant squamous or adenocarcinoma component as reviewed by the pathologist at MSKCC. However, if any element of small cell or neuroendocrine differentiation is present, the patients will be classified as small cell/neuroendocrine.
4. Confirmation of availability of sufficient tissue from a prior surgery for correlative studies is required prior to enrollment. Patients must have representative non-TCC or the urothelial tract FFPE archival tumor specimens (tumor blocks or 30 unstained slides; preference for tumor blocks). These samples may be submitted between the time of consent and the start of treatment. Patients with $<$ 30 slides may be enrolled after discussion with the principal or co-principal investigators, see Section 9.5.2 for more details.
5. Clinical evidence of metastatic (T4b, any N; any T, N2-3; M1) disease.
6. Life expectancy of 12 weeks of greater based on assessment by the treating investigator.
7. Evidence of measurable disease by RECIST 1.1.
8. Patients with small cell carcinoma must have progressed after at least one prior systemic therapy. Patients with squamous cell carcinoma or adenocarcinoma may be previously

untreated or have progressed after prior systemic therapy. Chemotherapy administered in conjunction with primary radiation as a radio-sensitizer WILL be counted as a systemic chemotherapy regimen. NOTE: There is no maximum number of prior treatments allowed.

9. Patients with brain metastases are allowed onto the study as long as patients have completed their treatment for brain metastasis, no longer require corticosteroids, and are asymptomatic. Subjects with neurological symptoms should undergo a head CT scan or brain MRI to exclude brain metastasis, at the discretion of the treating physician.

10. Eastern Cooperative Oncology Group (ECOG) performance status of 0-1

11. Adequate normal organ and marrow function as defined below:

- Hemoglobin \geq 9.0 g/dL
- Absolute neutrophil count (ANC) $\geq 1.0 \times 10^9/L$ (≥ 1000 per mm 3)

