14.4 Exploratory analyses

Listed below are immune related hypotheses and the plan for exploratory analyses. Additional or different investigational methods will be used to characterize and measure components of the immune response based upon the latest available technology at the time of analysis. Specimens will also be stored for future studies related to non-TCC of the urothelial tract immunity for those patients who have consented to an institutional biobanking protocol (e.g. 06-107, 12-245, etc). If tissue availability or funding is limited, assay priority will be determined at the investigators discretion.

The exploratory hypotheses listed below are hypothesis generating. As such, all four of the exploratory analyses will be descriptive and graphical in nature. To test the associations between binary CBR or subtypes and biomarkers we will use Fisher's exact or Wilcoxon rank sum tests for binary or continuous variables respectively.

Immune Hypothesis 1: The tumor microenvironment will vary based on the histologic subtype of non-TCC of urothelial tract.

Proposed biomarker evaluation: Analysis of immune infiltrate will be performed using immunohistochemistry (IHC), immunofluorescence (IF), and computational approaches based upon RNA sequencing data. Immune regulatory molecules and populations of cells analyzed may include, but will not be limited to PD-L1, CD4, CD8, Tregs, B cells, macrophages, and dendritic cells and expression of biologically relevant/phenotypic markers thereof. The Ventana SP263 assay (performed in accordance with the package insert on the Ventana Benchmark platform (Ultra or XT) should be used to measure PD-L1.

Immune Hypothesis 2: The composition and phenotype of the tumor microenvironment at baseline will correlate with the clinical benefit rate (CBR).

Proposed Biomarker Evaluation: See immune hypothesis 1.

Immune Hypothesis 3: High T cell clonality in the tumor plus peripheral expansion of dominant tumor-resident T cell receptor clones will be associated with the CBR.

Proposed Biomarker Evaluation: We will perform high throughput DNA sequencing of the CDR3 region of the TCR beta chain in baseline tumors and pre- and post-treatment peripheral blood.

Immune Hypothesis 4: High levels of myeloid derived suppressor cells (MDSCs) and T regulatory cells (Tregs) in the peripheral blood and high levels of immunosuppressive tumor associated myeloid cells and T regulatory cells in will correlate with a decreased CBR.

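### Specimen exposure to chemotherapy may differ between small cell and the other histologies, and the planned subtype tests have no step that would show it

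*Combined protocol and SAP*

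**What the plan says.** **Eligibility.** Inclusion criterion 8 (Section 6.2) says "Patients with small cell carcinoma must have progressed after at least one prior systemic therapy". Squamous and adenocarcinoma patients may be previously "untreated or have progressed after prior systemic therapy". Section 3.4 gives the reasoning and repeats the rule for small cell: "while patients with small cell/neuroendocrine must have been previously treated".

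**Tissue.** Inclusion criterion 4 states: "Confirmation of availability of sufficient tissue from a prior surgery for correlative studies is required prior to enrollment". Section 9.5.2 accepts transurethral resections, cystectomy specimens and several kinds of biopsy. Sections 8.1 and 9.5.2 rule out biopsies done only for research. No section supplied sets the timing of the specimen relative to earlier systemic therapy. Section 9.5 refers collection details to a laboratory manual (Appendix 6) that is not in the text reviewed.

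**Question and test.** The first exploratory objective (Section 2.1) is "To determine differences in the immune microenvironment between bladder cancer histologies". Immune Hypothesis 1 (Section 14.4) is "The tumor microenvironment will vary based on the histologic subtype of non-TCC of urothelial tract". The method is "To test the associations between binary CBR or subtypes and biomarkers we will use Fisher's exact or Wilcoxon rank sum tests", with no stratification, restriction or covariate for prior therapy. Section 14.4 also says that "all four of the exploratory analyses will be descriptive and graphical in nature". Hypotheses 2 and 3 describe the same tissue as baseline tissue.

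**The concern.** No chemo-naive small cell patient can enrol, while any share of the other patients may be chemo-naive. Section 3.4 adds that guidelines send muscle-invasive squamous and adenocarcinoma directly to cystectomy without neoadjuvant chemotherapy, and that small cell disease is chemotherapy sensitive. It is therefore plausible that small cell specimens were taken after chemotherapy more often than the others.

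If so, a marker that responds only to chemotherapy would differ between small cell and the other histologies, and the planned test would credit the difference to histology. Nothing in the plan would tell a reader whether this had happened, because specimen timing is neither defined nor used. The risk is an exploratory finding that points later work at the wrong cause.

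**Working it through.** **The plan's own figure.** The plan gives no operating figure for the histology comparison. The only number borrowed from it is the total of 27 (Sections 4.2 and 14.2). With 13 then 14 patients, continuation on at least 1 response and success on at least 4, the probability of declaring success is

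P(p) = Σ (x = 1 to 13) C(13,x) pˣ (1−p)¹³⁻ˣ · P[Bin(14,p) ≥ 4−x].

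This gives 0.0416 at p = 0.05 and 0.8011 at p = 0.20, so the stated design reproduces.

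**Assumptions for the comparison (not in the documents).**
- 9 small cell versus 18 other specimens (9 + 18 = 27), with the other two histologies pooled. Section 14.4 does not specify this contrast.
- A normally distributed marker with no true histology effect.
- Exposure shifts the marker by d = 0.5 or 1.0 SD.
- A two-sided 5% benchmark. Section 14.4 sets no significance level.

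**Bias.** Let qS and qO be the exposed shares of small cell and other specimens. The expected difference between groups is d × (qS − qO).
- d = 1, qS = 1, qO = 0.25: 1 × (1 − 0.25) = 0.75 SD.
- d = 1, qS = 0.5, qO = 0: 1 × (0.5 − 0) = 0.50 SD.
- qS = qO: zero for any d.

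**False-positive rate of the unstratified Wilcoxon test** (10,000 simulated trials per setting):

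| Small cell exposed | Others exposed | d = 0.5 SD | d = 1.0 SD |
|---|---|---|---|
| 100% | 0% | 19.3% | 61.8% |
| 100% | 25% | 12.8% | 36.2% |
| 100% | 50% | 7.8% | 17.3% |
| 100% | 75% | 4.9% | 7.4% |
| 100% | 100% | 4.4% | 4.5% |
| 50% | 0% | 8.0% | 18.9% |
| 50% | 25% | 5.5% | 8.2% |
| 50% | 50% | 4.5% | 4.7% |
| 0% | 0% | 5.0% | 4.8% |

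**Varying the small cell share, with the others held at roughly 20-50% exposed** (4 to 9 of 18 is 22% to 50%), over d = 0.5 to 1.0 SD:
- all 9 small cell specimens exposed: about 8-40%;
- 6 of 9 (67%): about 3-13%;
- 4 of 9 (44%, close to balance): about 2-5%.

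**After stratifying by exposure.** With all small cell specimens exposed, the stratified Wilcoxon (van Elteren) test rejects in 4.9% to 5.8% of null trials.

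**Price in power.** For a true 1 SD histology difference, power is about 61% unstratified and about 30-60% stratified, depending on how far the strata overlap. If all small cell tissue is exposed, the unexposed stratum contains no small cell specimen and contributes nothing. The comparison is then 9 small cell against the exposed others only. An ordinary rank sum test restricted in that way has power 24%, 44% and 57% against 4, 9 and 14 others. Its actual error is 3.3%, 3.6% and 4.6%, so it is conservative at the smaller sizes.

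**The case against.** The strongest reply is that eligibility describes the patient at enrolment, while the marker is measured in tissue that may be years older. A small cell patient's specimen may be a resection taken before any chemotherapy, and no section says otherwise. This stands. A reader might infer that the eligibility rule makes histology and chemotherapy exposure inseparable in this trial. The documents do not support that. Exposure may be balanced, and squamous and adenocarcinoma patients may also be pretreated, so like-with-like comparison may be possible. The highest rates above depend on every small cell specimen being post-chemotherapy, which is an assumption.

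Three further limits also stand. The rule creates no structural imbalance between squamous and adenocarcinoma. The analyses are declared hypothesis generating and descriptive, with no decision attached. And Hypothesis 2 relates the microenvironment directly to clinical benefit without using the Hypothesis 1 result, so it should not be said that an error in one carries into the other.

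What the reply does not remove is the gap itself. Section 14.4 names tests as well as graphics, and neither the tests nor the text supplied would reveal whether exposure was balanced. The exploratory label lowers the weight of the point but does not correct a misattributed difference.

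**Conclusion.** The point holds as a minor one. Specimen exposure to chemotherapy may differ between small cell and the other histologies. If it does, the unadjusted subtype tests mix exposure with histology for that contrast. Whether it does cannot be told from the documents.

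The size runs from no inflation, when exposure is balanced, through about 3-13% false positives when two thirds of small cell specimens are exposed, to about 8-40% when all are. These figures rest on the assumed 9 versus 18 split, a 0.5 to 1.0 SD shift and about 20-50% of the other specimens being exposed. The primary response-rate design does not use this comparison and is unaffected.

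**What to change.** In Section 14.4:

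1. Record the date of each archival specimen. Class the specimen as taken before or after first systemic therapy, using the previous treatments already collected at screening (Section 10.0 table).
2. Report Immune Hypothesis 1 by that class, with a stratified Wilcoxon or exact stratified test, alongside the planned unstratified test.
3. Where the strata do not overlap, state that the difference cannot be separated from prior therapy.
4. Describe the tissue as archival, not as baseline.

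Two additions are best avoided. A rule to take the most recent specimen would favour post-chemotherapy tissue in pretreated patients, which includes every small cell patient, and could widen the imbalance. Restriction to pre-therapy specimens should not be the main analysis, because it could leave no small cell specimens at all.

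The cost is one derived variable, one extra date if the laboratory manual does not already capture it, and lower power for the stratified result (about 30-60% against about 61% for a true 1 SD difference). No new procedure or patient is needed.
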